### **7.6 Device Deficiency Reporting**

Device deficiency is defined as the inadequacy of a medical device with respect to its identity, quality, durability, reliability, usability, safety, or performance. Device deficiencies include malfunctions, use errors, and inadequacy in the information supplied by the manufacturer including labelling. In this clinical trial we will document any product or material defects, potential wrong application (via pant fit images), leaking/failure of overnight absorbent pants and all AEs /ADEs.

All device deficiencies of the investigational products will be documented throughout the clinical trial and managed by the sponsor in accordance with written procedures for the control of a non-conforming product. The sponsor shall take, where applicable, and appropriate, and corrective actions to protect the safety of subjects, users, and other persons. Device deficiencies of the comparator, if applicable, shall be documented.

Device deficiencies that did not lead to an adverse event, but could have led to a serious adverse device effect:

1. if either suitable action had not been taken
2. if intervention had not been made, or
3. if circumstances had been less fortunate

shall be reported to the sponsor, who will prepare the needed Clinical Evaluation Report documentation and report the potential risk to the EC/IRB and national authorities as applicable. The sponsor will decide whether the risk analysis needs to be updated and assess whether preventative or corrective action is required.

## **7.7 Investigator's Final Report**

The Investigator will provide a Final Report within approximately 30 days from the completion of the in-life phase of the clinical trial. The report will consist of a description of the conduct of the clinical trial including subject enrollment, subject demographics, protocol deviations, subject dropouts, and a discussion of AEs. Data analyses or data interpretation, if any, may be included in a separate document.

## **7.8 Records Retention**

The Investigator(s) must retain the subject identification codes, Informed Consent documentation, CRFs, medical records, and other source data for a minimum of 2 years after clinical trial completion. The Investigator(s) must receive written authorization from the Sponsor before destroying any clinical trial document.

The Investigator(s) will make the records available for inspection and copying upon the request of an authorized employee of a government authority or the Sponsor, at reasonable times.

In the event the Investigator(s) retires, relocates, or for any other reason withdraws from the responsibility for maintaining records for the period of time required, custody of the records may be transferred to another person who will accept responsibility for the records. Notice of such a transfer must be given in writing to the Sponsor.

The sponsor will maintain clinical records according to P&G Records Management Guidelines.

## **7.9 Publications**

All data collected during this clinical trial is the sole responsibility of the Sponsor. No publication by the site or any of the non-employees of the sponsor is allowed from the results of this clinical trial. The Sponsor reserves the right to withhold consent for publications due to the confidential nature of the data. Subjects will be identified only by the assigned four-digit code and no identifiable personal information will be included.

# **8. Sponsor Clinical Trial Management**

## **8.1 Data Quality Assurance**

The following steps will be taken to ensure the accuracy, consistency, completeness, and reliability of the data:

- Source/CRF review,

- Data management quality control checks, and
- Statistical quality control checks.

In addition, a representative from the Sponsor may conduct periodic audits of clinical trial processes, including, but not limited to, a review of the Investigator's Trial Master File (TMF), Standard Operating Procedures (SOPs) pertaining to the clinical trial, and training records of staff involved.

#### **8.1.1 Monitoring**

Prior to the commencement of the clinical trial, an initiation meeting will be held with the appropriate clinical trial site personnel to review the objectives and procedures of the clinical trial and any other training needs associated with the clinical trial and protocol execution.

This clinical trial will be monitored by Sponsor representatives at all stages of conduct from inception to conclusion in accordance with and ICH GCPs chapter 5.

#### **8.2 Clinical Trial Termination**

The clinical trial will be terminated upon completion of all subject treatments and evaluation. The Sponsor may discontinue the clinical trial at any time. In any case where this happens, the Principal Investigator and/or designee will return all clinical trial supplies, and equipment to the Sponsor. In addition, all data which has been collected up to that point will be turned over to the Sponsor at that time.

#### **8.3 Sponsor's Final Report**

A final report will be prepared by the Sponsor at the conclusion of this clinical trial. The Sponsor's final clinical trial report will summarize the method, data, and conclusions. Source data may be retained by the testing facility. The original source data will be maintained according to the Principal Investigator's standard operating procedure. A copy of the source documents may be obtained upon request of the clinical trial Sponsor.

**Attachment A****Risk Assessment****Product Safety**

No safety issues are anticipated with this clinical trial as outlined. Children participating in this clinical trial are using marketed products or products that are close to being marketed. From products purchased on the market, we can assume that they have been tested and evaluated for their safety in daily use. Children will be asked to use these products as intended.

For the NJ EU test products, a full risk assessment according to the ISO 14971 standard is being conducted and will be summarized in a separate document before the start of the clinical trial.

The P&G company has a 20+ year history of baby diaper clinical data (0-36 months) to show that our diaper and pant technology is safe to use and effective for managing urine gushes in a baby and toddler population. The P&G company also has adult (18+ years) female incontinence products in the EU market, including absorbent heavy incontinence pants, that are classified as Class 1 Medical Devices, which were demonstrated to be safe to use and effectively manages urine gushes of adults as seen in the statement of compliance from the CER report dated Feb 2020 [1].

[REDACTED] P&G markets a training pant (BabyDry Pants S7) in the EU. Based on the Post Market Safety Surveillance data of similar products in the EU and US market (BabyDry Pants, FemCare AI Pants, [REDACTED]), we have reason to believe that the NJ EU product will have no safety related issues when used as an overnight pant for children aged 4-12 years, based on skin and health related AEs. [2]

Based on our current knowledge about this product and similar marketed products, we conclude the following statement, which will be updated based on the outcome of this clinical trial:

**Statement of Compliance for Children's Nocturnal Enuresis Devices**

*It is understood that similarity between intended use and indications for use exists between the Procter & Gamble Children's Nocturnal Enuresis Devices and competitor products. Such devices serve as morphotypes. Procter & Gamble Children's Nocturnal Enuresis Devices when used under the conditions and for the purposes intended, will not compromise the clinical condition or the safety of patients, or the safety and health of users or, where applicable other persons. The benefit of Procter & Gamble Children's Nocturnal Enuresis Devices outweighs the risks associated with the product.*

*Clinical risk identified in risk management has been adequately addressed for use in this clinical trial. This risk associated with the product is very minimal compared to the benefits of the product. Clinical investigation performed on similar Procter & Gamble [REDACTED] pants identified no serious adverse events and no withdrawals due to adverse events. Procter and Gamble [REDACTED] pants were well tolerated by the subjects with no product-related adverse events.*

*Procter & Gamble Children's Nocturnal Enuresis Devices are very simple devices and easy to use. No specific training is required to use this product. There is full consistency between current knowledge/ the state of the art, the available clinical data, the information materials supplied by the manufacturer, and the risk management documentation for Procter & Gamble Adult Children's Nocturnal Enuresis Devices.*

As with any absorbent pant or diaper, it is possible in exceptional cases that these products may cause skin reactions like redness, blisters, or sores. These skin reactions are usually temporary and usually need no medical treatment, nor are they dangerous to the health. The risk of allergies cannot be totally excluded but can be considered very unlikely for these products. For subjects in this clinical trial, we do not expect any further risks apart from potential skin reactions (like redness). In case your child has some skin reactions (redness, swelling or blisters) during this test that concerns you, please contact the clinical trial personnel.

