## **3.7 Assessment and Collection Details**

### **3.7.1 Skin Rash [REDACTED] Grading [REDACTED]**

The parent/legal guardian will use the following multi-level grading scale to assess rash [REDACTED] in the following regions of the pant area: hips, genital area, buttock area, perianal area (only rash grading):

- None
- Mild
- Moderate
- Severe

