#### **7.5.1 Adverse Event and Adverse Device Effect Reporting**

[REDACTED] the parent/legal guardian will be asked twice daily about their child's health and medication intake. Based on the information provided, Sponsor and PI will determine if it is appropriate to record as an Adverse Event or Adverse Device Effect and will contact the parent/legal guardian for more information. Such an occurrence does not necessarily have to have a causal relationship with product use. Due to the nature of this clinical trial, skin irritation in the pant area (diaper rash) will not be documented as an Adverse Event or Adverse Device Effect given it is one of the end points of interest for the clinical trial. However, if a skin reaction occurs in the pant area which causes the parent/legal guardian to seek medical attention, outside the normal follow-up given to the child within the clinical trial, this will be documented and followed in the same manner as other Adverse Events or Adverse Device Effects.

[figure not shown]
The Investigator or designee will review each Adverse Event Report and complete the form based on the following decision charts:

*Chart 1: Categories of ADE and AEs*

Adverse events	Non-device-related	Device- or investigational procedure-related	
Non-serious	Adverse event (AE) a (3.2)	Adverse device effect (ADE) c (3.1)	
Serious	Serious adverse event (SAE) b (3.45)	Serious adverse device effect (SADE) (3.44)	
		Anticipated	Unanticipated
		Anticipated serious adverse device effect (ASADE) c (3.1, Note 1 to entry)	Unanticipated serious adverse device effect (USADE) (3.51)

a Includes all categories.  
b Includes all categories that are serious.  
c Includes all categories that are related to the device or the investigational procedure.

Chart 2: AE categorization flow chart

The Investigator or designee will review each Adverse Event Report and complete the form based on the following definitions:

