## Skin Health

6. Parental skin rash perception (none/mild/moderate/severe). We will calculate the cumulative number of [REDACTED] scores [REDACTED]

[REDACTED]  
[REDACTED]  
[REDACTED].

[REDACTED]  
[REDACTED]  
[REDACTED]  
[REDACTED]  
[REDACTED].

[REDACTED]  
[REDACTED]  
[REDACTED]  
[REDACTED]  
[REDACTED].

[REDACTED]  
[REDACTED]  
[REDACTED]  
[REDACTED].

10. Skin irritation perception from child (burning/itching/ stinging/tingling/feeling of heat). We will calculate the cumulative number of skin irritation scores [REDACTED]

[REDACTED]  
[REDACTED]  
[REDACTED].

[REDACTED]  
[REDACTED]  
[REDACTED]  
[REDACTED]  
[REDACTED].

[REDACTED]

[REDACTED]  
[REDACTED]  
[REDACTED].

**Protocol Amendment I  
CSD2021096/ NCCI #12-2103**

**OVERNIGHT PANT SAFETY-IN-USE DIARY CLINICAL TRIAL FOR CHILDREN WITH NOCTERNAL  
ENURESIS**

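### On its natural reading, Section 7.5.1 lets a pant-area blister, sore or swelling managed without outside medical care stay out of the AE/ADE listing, and no visible field separates it from a rash grade

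*Combined protocol and SAP*

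**What the plan says.** **Attachment A (Risk Assessment, paragraph after the Statement of Compliance).** The sponsor accepts that "it is possible in exceptional cases that these products may cause skin reactions like redness, blisters, or sores". It describes these reactions as generally passing and seldom in need of treatment. Parents are told: "In case your child has some skin reactions (redness, swelling or blisters) during this test that concerns you, please contact the clinical trial personnel". No form or record is tied to that contact.

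**Section 7.5.1.** The exclusion reads: "skin irritation in the pant area (diaper rash) will not be documented as an Adverse Event or Adverse Device Effect". The reason given is that irritation is already an endpoint. The exception follows: "if a skin reaction occurs in the pant area which causes the parent/legal guardian to seek medical attention", outside the normal follow-up within the trial, then "this will be documented and followed in the same manner as other Adverse Events or Adverse Device Effects".

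**Skin endpoints.** Section 3.7.1 says "The parent/legal guardian will use the following multi-level grading scale to assess rash", with levels none, mild, moderate and severe by region; part of the sentence is redacted. SAP Skin Health item 6 is "Parental skin rash perception (none/mild/moderate/severe"), with redactions after it. Child perception (Section 3.7.8 and SAP item 10) covers sensations only: burning or stinging, itching or tingling, warmth.

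**Safety analysis.** SAP item 1 lists product-related ADEs and AEs for both treatment periods. A recommendation on whether the test pant is comparable in safety to the current product is then made from the reported AE and ADE data.

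**The concern.** The reason for the exclusion is that the event is measured elsewhere. That works for redness, which the rash grade measures. It is not shown to work for the other reactions that Attachment A names, because no visible item records the type of lesion. A patch of redness and a blister can receive the same grade.

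The exception is also unlikely to pick up many of these cases. It needs medical attention outside the trial, while the sponsor's own text expects that most such reactions need no treatment. A parent who follows Attachment A and calls the site, and whose child is then looked after by the site, may never meet the trigger.

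The primary objective is to confirm tolerability (Section 2). Attachment A says its compliance statement will be updated from this trial's outcome, and that statement already cites the absence of product-related adverse events for similar pants. A low or empty AE/ADE listing here could partly reflect the recording rule.

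**Working it through.** **Step 1. Set the terms side by side.**

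| Reaction | Named in Attachment A | Visible endpoint that identifies it | AE/ADE under 7.5.1 without outside care |
|---|---|---|---|
| Redness | yes | rash grade | excluded, with a reason that fits |
| Blister | yes | none by type | not clearly required |
| Sore | yes | none by type | not clearly required |
| Swelling | yes (instruction to parents) | none by type | not clearly required |

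Section 7.5.1 uses two terms. The exclusion is worded for irritation (diaper rash). The exception is worded for a skin reaction, which is Attachment A's term for redness, blisters and sores. If a skin reaction has to lead to medical attention before it is documented, the natural inference is that one without such attention need not be. The text does not say so outright, so the status of these lesions is undefined.

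**Step 2. Illustrate the size.** The plan has no figure to reproduce: Section 4.2 says the sample size was set on practical grounds, and no event rate is stated.

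Inputs:
- n = 32 children (Protocol Amendment 1), all assumed to wear the test pant.
- r = per-child risk of such a lesion during the test-pant period. Assumed: 0.1%, 1%, 5%.
- s = share of cases that lead to outside medical attention. Assumed: 20%, with 10% to 50% as a range.
- Children are treated as independent, and the medical-attention exception as the only recording route.

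Formulas:
- P(at least one occurs) = 1 − (1 − r)^32
- P(at least one recorded) = 1 − (1 − rs)^32
- P(at least one occurs, none recorded) = (1 − rs)^32 − (1 − r)^32

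Results at s = 20%:

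| r | (1 − r)^32 | (1 − rs)^32 | At least one occurs | At least one recorded | Occurs, none recorded |
|---|---|---|---|---|---|
| 0.1% | 0.9685 | 0.9936 | 3.2% | 0.6% | 2.5% |
| 1% | 0.7250 | 0.9379 | 27.5% | 6.2% | 21.3% |
| 5% | 0.1937 | 0.7250 | 80.6% | 27.5% | 53.1% |

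With s from 10% to 50%, the last column runs from 2.8% to 1.6% at r = 0.1%, from 24% to 13% at r = 1%, and from 66% to 25% at r = 5%.

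**Step 3. Read the illustration with care.** Attachment A speaks of exceptional cases, so the lower rows are closer to the sponsor's expectation. Any other route that catches a case lowers the last column.

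**The case against.** A reader might infer that blisters, sores and swelling cannot be counted anywhere in this trial, or that the plan grades nothing but rash. The documents support neither.

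- **Some reactions are recorded.** Those leading to outside medical attention are documented under 7.5.1 and, if product related, listed under SAP item 1.
- **The exclusion is narrow.** It is worded for diaper rash. Section 7.5 otherwise documents changes in health regardless of causality, so a site could record a blister as an AE.
- **Partial routes exist.** The twice-daily questions (Section 3.3.3) ask about other illness, injury, medication and creams in the pant area. Under 7.5.1 the sponsor and the investigator review the health and medication answers and contact the parent. Section 3.2.2 provides contact at least weekly.
- **Redactions block any claim about what is missing.** In Section 3.7.1 the perianal area is marked for rash grading only, so another item must be graded in the other regions. Section 3.2.1 trains parents on imprints and marks. Section 3.3.4 has several redacted items, including the content of the observations at pant removal, and SAP Skin Health is largely redacted.
- **Tolerability rests on several sources.** A sore could still appear as a higher rash grade or as reported burning.

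All of this stands. It leaves one point: none of the visible routes requires a blister, sore or swelling to be documented as an AE/ADE when no outside care is sought. A redacted lesion field would settle identification, but would not settle AE/ADE status under the visible wording of 7.5.1.

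**Conclusion.** The concern holds as a gap in a stated recording rule. The status of blisters, sores and swelling in the pant area is undefined in 7.5.1, and its natural reading lets cases managed at home or by the site stay out of the listing behind the SAP item 1 recommendation. No visible field separates them from a rash grade.

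The size is uncertain. Over the assumed risks of 0.1% to 5%, with 20% seeking outside care, the chance that at least one case occurs and none enters through the exception runs from about 2.5% to 53%. Both rates are assumptions. The conclusion rests on the wording of 7.5.1 and Attachment A, which should be reconciled, and not on these figures. The change is cheap and worth making.

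**What to change.** 1. In Section 7.5.1, limit the exclusion to redness or diaper rash that the rash grade covers. State that blisters, sores or broken skin, and swelling in the pant area are documented as AE/ADE for whichever product was worn, whether or not outside care is sought. Include those reported to the site under the Attachment A instruction.
2. In SAP item 1, list these reactions by product.
3. Check the redacted questionnaire items. Only if none already captures lesion type, add one tick item beside the rash grade: blister, sore or broken skin, swelling, none.

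The cost is a scope statement in 7.5.1, one listing line in the SAP and possibly one tick item in an existing questionnaire. The downside is a few more AE forms and a slightly less favourable event count. The change concerns recording only and leaves clinical management as it is.

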**Study Safety:**

For the twice daily questionnaire, the parent/legal guardian will be asked to touch the child's skin in the pant area. Parent/legal guardian will be instructed to wash their hands before and after for hygienic reasons.

Parent/legal guardian will be asked to use a pH meter to measure skin pH and a gskin device to measure skin hydration. The pH meter is made of glass and can break. Parent/legal guardian will be asked to take precautions when using the instrument to avoid the risk of glass breakage and not to use a broken device.

Parent/legal guardian will receive training on how to use these measuring devices correctly. They will be asked to ensure all instruments are switched off when not in use. These devices are not toys and should only be handled by an adult. Parent/legal guardian will be reminded to keep these devices out of the reach of children and pets. In addition, the associated chemicals (storage solution and buffer solutions) should be kept in a safe place. These solutions are not dangerous when swallowed.

In case the instruments get contaminated or dirty, parent should wipe with a provided alcohol wipe. They should not immerse any devices in water or rinse under running water. Parent/legal guardian will be instructed to disinfect all devices after use with an alcohol wipe to prevent bacterial growth.

**Attachment B**  
**Statistical Analysis Plan**

**Study Populations**

The Intent-to-treat (ITT) population is defined as all subjects who experienced the application of the assigned study product. The Per Protocol (PP) population includes subjects in the ITT population who have no serious inclusion/exclusion violations, no serious continuance criteria violations, no serious concomitant medication violations, and high study product compliance. The ITT population will be used for the safety analysis. Analyses of the Per Protocol population will be done to better understand the data.

Prior to the statistical analysis, all data will be checked for accuracy, completeness, and compliance to the study protocol. Subject evaluations will be checked for compliance to the study protocol regimen and subjects will be assessed for compliance to the protocol inclusion/exclusion criteria. Additionally, investigator comments will be assessed for extraneous factors that could affect the usefulness of the subject's data. Non-evaluatable observations and the rationale, along with the method for handling the observations will be documented by the sponsor prior to analysis of the data.

Period and carryover effects will be evaluated for potential influence on the results. Means will be plotted by periods to understand these effects.

Summary descriptive statistics will be provided for all parameters. Ninety-five percent confidence intervals (CIs) will be constructed for all clinical assessments for each treatment code. Any data reported as 'unable to evaluate' will be treated as missing and excluded from the analysis.

The methods used for the analysis will include but not be limited to a variety of parametric and non-parametric statistical methods based on the distribution/characterization of the data.

The following endpoints will be investigated.

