7. The use of skin products like lotions, oils, powders, creams, sunscreens, wet wipes and moisturizing bubble baths will not be allowed to be used in the pant area and thighs, unless needed for medical reasons. Use of these skin preparations will be captured in the daily questionnaire [REDACTED]  
[REDACTED].
8. After enrollment, parent/legal guardian will receive the following items:  
[REDACTED]  
[REDACTED]
  - [REDACTED]
  - Two coin-cell batteries as back-up
  - [REDACTED])
  - Kitchen scale (balance) with USB charging cable
  - [REDACTED]
  - Measuring tape
  - [REDACTED]
  - Written subject instructions
9. Parent/ legal guardian will participate in a training session on the following:
  - a. Review of [REDACTED] questionnaire
  - b. How to take photos using mobile phone [REDACTED]
  - c. How to assess rash, imprints/marks on the skin
  - d. [REDACTED])
  - e. [REDACTED]
  - f. [REDACTED]
  - g. [REDACTED]
  - h. How to weigh the pant
10. [REDACTED]  
[REDACTED]
11. Parent/legal guardian will be asked to begin completing the questionnaire (2x/day) for 45 days. The first 2 days will be considered practice days and data from day 1 and 2 will be considered non-evaluable.

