#### 3.3.1 Inclusion Criteria

Inclusion and Exclusion criteria will be assessed at the Enrollment visit in an individual conversation with parent/legal guardian (with child present).

Subjects are eligible for enrollment if the parent/legal guardian responds positively ("Yes") to the following questions:

- INCL01:** Have you read and understood the Informed Consent document?
- INCL02:** Is your child generally healthy? [excluding acute conditions such as flu/cold symptoms, diarrhea, fever, ear infection, etc.]
- INCL03:** Is your child 4-7 years of age?
- INCL04:** Does your child weigh approximately 37–63 pounds and fit into the test pant [Clinical trial personal to confirm fit]?
- INCL05:** Thinking of the past 3 months, does your child wet the bed at night at least once per week?
- INCL06:** Is your child currently using overnight pants or diapers?
- INCL07:** Is your child willing to use their usual and/or supplied overnight pant products every night for the duration of the study?
- INCL08:** Are you and your child willing to refrain from using wet wipes in the pant area for the duration of the clinical trial?
- INCL09:** Are you willing to refrain from enrolling your child in other clinical or consumer studies for the duration of this clinical trial?
- INCL10:** Are you and your child willing to refrain from using lotions, creams, ointments, oils, moisturizing bubble baths, powders, sunscreen and/or skin preparations in the child's pant area and on thighs for the duration of this clinical trial, unless required for medical reasons?
- INCL11:** Are you and your child willing and able to comply with all study instructions?
- INCL12:** Do you have an iPhone 7 (or higher) with iOS 13.0 operating system (or higher) or do you have an Android smartphone with operating system Android 9 (or higher) installed?
- INCL13:** [REDACTED]
- INCL14:** Are you able to fill in the required questionnaires in English?
- INCL15:** Are you willing to complete the [REDACTED] questionnaires twice daily for 6 weeks, once in the morning when removing the pant and once more in the evening when applying the pant?

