### 3.3.4 Data Measurement Collection

The following information will be collected twice daily (am/pm) [REDACTED]:

1. Leaks (If yes, parent/legal guardian will be asked to take an image of the wet stain on the pant and send the image to the site) [REDACTED]
2. [REDACTED]
3. [REDACTED]
4. [REDACTED]
5. Photos of pant on child [left hip, right hip, front, back] [REDACTED]
6. Parent/child assessment of rash [hips, genital, buttock, perianal] [REDACTED]
7. [REDACTED]
8. Pant weight (loaded pant mornings / fresh pant evenings)
9. Hours of pant wear
10. Pant contents [urine, both urine & BM, parent removed solid BM, nothing]
11. Number of pants used since last questionnaire
12. Observations during pant removal: [REDACTED]

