**Product Fit and Performance:**

2. Product performance in terms of urine leaking (yes/no). We will calculate the percentage of leaks from loaded pants only. When comparing both products, Ninjama EU option should not be [REDACTED] worse than current product).
3. [REDACTED]  
[REDACTED].
4. Pant fit images will be investigated by an expert grader to identify any application errors (e.g., applied wrong way) [REDACTED]

5. Images of the wet stain on the overnight pajama pant will help identify the size of the stain and where the pant was leaking. This will be compared with the pant fit images.

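### Must the SAP fix the unit of analysis and a within-child interval for the leak comparison?

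*Combined protocol and SAP*

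**What the plan says.** Attachment B, Product Fit and Performance, item 2, makes leaking a yes/no outcome and fixes the denominator: "We will calculate the percentage of leaks from loaded pants only". It then sets a comparative criterion that begins "When comparing both products, Ninjama EU option should not be" and continues into a redaction before saying worse than the current product. A closing bracket follows whose opening bracket is not visible.

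The general part of Attachment B provides intervals by product, "Ninety-five percent confidence intervals (CIs) will be constructed for all clinical assessments for each treatment code", and leaves the method open: "The methods used for the analysis will include but not be limited to a variety of parametric and non-parametric statistical methods", chosen according to the data. It also says "Period and carryover effects will be evaluated for potential influence on the results", with means plotted by period.

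Three other places govern how many pants a child can supply. Section 3.2.1, item 11, sets 45 days of questionnaires and adds "The first 2 days will be considered practice days and data from day 1 and 2 will be considered non-evaluable". Section 3.3.4, item 11, records "Number of pants used since last questionnaire". INCL05 asks "does your child wet the bed at night at least once per week". Protocol Amendment 1 sets the sample at about 32 children, about 16 per sequence.

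**The concern.** Each child uses both products, so the natural quantity is the within-child difference in leak percentage. Two separate per-product intervals cannot give its precision, because they carry no information on how far a child's tendency to leak is shared between products. Pants also repeat within a child. If they were counted as independent, each per-product interval would be too narrow, and the interval for the difference could be too narrow as well.

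The unit also affects the estimate. A percentage pooled over pants weights frequent wetters more heavily than an average of per-child percentages does. If the product difference varied with wetting frequency, the two summaries would differ. At stake is whether the leak criterion is judged on an honest measure of uncertainty and on a quantity fixed in advance.

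**Working it through.** The plan gives no precision or power figure to reproduce. Section 4.2 rests the sample size on practical limits. The arithmetic below is therefore illustrative.

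**Inputs.** From the documents: N = 32 children. Nights per product are (45 − 2)/2 = 21.5 if split evenly. If Visit 2 falls exactly three weeks after Visit 1 (Section 3.2.5) and both practice days fall in the first period, they are 21 − 2 = 19 and 45 − 21 = 24. INCL05 implies at least about 3 wet nights in three weeks. Assumed: loaded pants per child per product, n, uniform on 3 to 21; leak rate p; within-child correlation ICC; correlation ρ of a child's leak propensity between products.

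**Per-product interval.** E[n] = 12 and Var[n] = (19² − 1)/12 = 30, so E[n²] = 144 + 30 = 174 and E[n²]/E[n] = 14.5. The design effect is 1 + 13.5 × ICC, that is 1.68, 2.35 and 3.70 at ICC 0.05, 0.1 and 0.2. Coverage of an interval ignoring clustering is 2Φ(1.96/√DE) − 1, or about 87%, 80% and 69%.

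**Interval for the difference.** The true variance of the pooled difference, divided by the variance assuming independent pants, is 1 − ICC + 14.5 × ICC × (1 − ρ). Coverage of the unpaired pant-level interval follows by the same formula:

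| ICC | ρ = 0 | ρ = 0.5 | ρ = 0.9 | ρ = 1 |
|---|---|---|---|---|
| 0.1: ratio | 2.35 | 1.63 | 1.05 | 0.90 |
| 0.1: coverage | 80% | 88% | 94–95% | 96% |
| 0.2: ratio | 3.70 | 2.25 | 1.09 | 0.80 |
| 0.2: coverage | 69% | 81% | 94% | 97% |

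A beta-binomial simulation at leak rates of 5, 10 and 20% (6,000 runs per setting) gives 79–81%, 86–87%, 94–95% and 96% for the first row, and 69%, 78–80%, 92–93% and 97% for the second. A paired interval clustered by child covers 94–96% throughout, in runs with no period effect and no dropout.

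**Width at p = 10%.** With 32 × 12 = 384 pants per product, the pant-level half-width is 1.96 × √(2 × 0.09/384) = 4.2 points. At ICC 0.2 the clustered value is 4.2 × √2.25 = 6.4 points at ρ = 0.5 (6.7 in the simulation, which uses a t quantile) and 4.2 × √0.80 = 3.8 at ρ = 1.

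**Effect of the unit.** Suppose the difference rises linearly from 0 to 10 points as n goes from 3 to 21: d = 10(n − 3)/18. The per-child mean is 5.0. The pooled value is (10/18) × (174 − 36)/12 = 6.4. With the gradient reversed, the pooled value is 10 − 6.4 = 3.6 and the per-child mean is still 5.0. With no gradient the two agree.

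**What the text supports.** These results apply only if the analyst ignores clustering, and no sentence says that. A pooled percentage is a point estimate and does not fix its variance. The per-product interval sentence refers to clinical assessments. Section 2 uses that term for skin, whereas leaks stand under a separate performance heading, so a per-product leak interval may never be computed. The comparison rule in item 2 is partly redacted, and the unmatched bracket shows that more text stood there.

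**The case for a change.** The case for a change is that the interval and methods sentences in the general part of Attachment B show no redaction, and they name only per-product intervals and an open list of methods. A crossover with a comparative criterion should state its contrast, and adding one costs a few lines and no data. The choice of unit can matter a good deal. Suppose half the children have 3 loaded pants and half 21, with test leak rates of 5% and 20% against own-product rates of 15% and 10%. The pooled difference is (3×5 + 21×20)/24 − (3×15 + 21×10)/24 = 18.1 − 10.6 = 7.5 points, while the per-child mean difference is 12.5 − 12.5 = 0. Blinding the statistician until database lock, as Amendment 1 intends, does not stop the unit being chosen afterwards.

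Part of this stands. The unredacted text does not state pooled or per-child aggregation, or how repeated nights are handled, and writing it down would do no harm. But the 7.5-point example needs the product effect to reverse between light and heavy wetters, which nothing in the documents suggests. Nor can a paired comparison be called absent when the sentence that would carry it is blacked out. Clustering by child is no complete cure either: simulated child-clustered per-product intervals cover only 87–92% at a 5% leak rate with 32 children.

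**Conclusion.** No change to the plan follows. The visible SAP leaves unwritten the level of aggregation and the paired method for one performance outcome. That is a gap which a statistician analysing a crossover fills as a matter of course, and the commitment to examine period and carryover effects shows that the design is in view. The documents do not show that the planned analysis would be wrong or worse than the alternative.

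The possible harm cannot be sized from the documents. For ICC 0.1 to 0.2, coverage of an unclustered interval for the difference runs from 69% when propensities are unrelated between products to 97% when they are fully shared. Leak rate, ICC, ρ and pant counts are all assumed. The consequence is also limited: the primary objective is tolerability judged on a body of evidence, leaks bear on performance and the secondary dry-bed objective, and the sample size has no statistical basis that a wider interval would upset. This conclusion is limited to the visible text. Protocol Amendment 2, named in the contents list, was not available to check.
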